### **11.4. POSTERIOR SEGMENT EXAMINATION**

Posterior segment examination endpoints (posterior segment abnormalities, presence of posterior vitreous detachment, presence of retinal hemorrhage/detachment, vitreal hemorrhage density and vitreous cells evaluation) will be summarized separately for the study eye and the fellow eye by

## Statistical Analysis Plan

---

treatment group and protocol specified time points for the MITT population, using summary statistics for categorical variables.

All other ophthalmology data collected based on Slit Lamp and Dilated Binocular Indirect Ophthalmoscopy examinations but not discussed in other sections of the SAP will be listed by treatment group.

### **11.5. LOCS III LENS**

The observed and change from baseline values for each of the 4 endpoints (nuclear opalescence, nuclear color, cortical cataract and posterior subcapsular cataract) will be summarized by treatment group and protocol specified time points, for those subjects with LOCS III performed during the study. The denominator for this summary will be the subset of phakic subjects who have a LOCS III assessment performed at any time during the study. The number of pseudophakic and aphakic subjects will also be presented.

All individual LOCS III data will be listed by treatment group. The listing will include change from baseline values. If no baseline value is collected and the baseline anterior segment assessment confirms no opacity in the lens then a value of 0.1 will be used for baseline and the change from baseline value will be flagged to identify the imputation.

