Blood Draw – Genotyping (if applicable) ^C				x							
Vital Signs ^D	x	x	x	x	x	x	x	x	x	x	x
Urine Pregnancy Test ^E				x	x	x	x	x	x	x	x
BCVA	x	SE	SE	SE	SE	SE	SE	SE	x	SE	x
LL-BCVA	x	SE	SE	SE	SE	SE	SE	SE	x	SE	x
IOP Measurement	x	SE	SE	SE	SE	SE	SE	SE	SE	SE	x
Slit Lamp Examination	x	SE	SE	SE	SE	SE	SE	SE	SE	SE	x
LOCS III Lens Grading ^F	x	SE	SE	SE	SE	SE	SE	SE	SE	SE	x
Dilated Binocular Indirect Ophthalmoscopy	x	SE	SE	SE	SE	SE	SE	SE	SE	SE	x
SD-OCT ^G	x			SE		SE			SE		x
Fundus Autofluorescence Photographs (FAF) ^G	x			x		x			x		x
Infrared Reflectance (IR) ^G	x			x		x			x		x
Digital Color Fundus Photographs (DCFP)	x										x
Fundus Fluorescein Angiograms (FFA)	x										x
Study Eye Determination	x										
Randomization		x									
APL-2 administration or Sham injection		x		x	x	x	x	x	x		
Post-Injection Assessment ^H		x		x	x	x	x	x	x		
Concomitant Medication / Adverse Events		x	x	x	x	x	x	x	x	x	x

SE= Study eye only

A. On visit 2, review inclusion/exclusion and confirm eligibility by the Central Reading Center (CRC).

B. Includes HCG for WOCBP and FSH/LH blood for postmenopausal females at screening.

C. Genotyping will only be performed at selected sites.

D. On injection visits, vital signs will be measured within approximately 1 hour prior to dosing and within 30 minutes after dosing.

E. Only WOCBP

F. If a lens finding is noted during the slit-lamp examination, at any visit, then the finding should be further characterized with LOCS III. All subsequent visits for that patient should include LOCS III.

G. On injection visits, SD-OCT, FAF and IR should be performed before APL-2 (or Sham) administration. IR will only be done at selected clinical sites with Heidelberg Spectralis® system.

H. Initial assessment must be done within 15 minutes after dosing. Additional assessments should be done every approximately 30 minutes, if needed.

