### **4.3.5. LOCS III Lens**

If an abnormal lens finding is noted during the anterior segment (slit lamp) examination, at any visit, then the finding should be further characterized with LOCS III. All subsequent visits for that subject will include LOCS III. LOCS III is used to grade the severity of age-related cataracts. LOCS III

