## Statistical Analysis Plan

---

grading will not be assessed for pseudophakic and aphakic subjects as they do not have opacity.

For the subset of subjects having this additional ophthalmology assessment, the endpoints are:

- [NO] nuclear opalescence (range 0.1 to 6.9)
- [NC] nuclear color (range 0.1 to 6.9)
- [C] cortical cataract (range 0.1 to 5.9)
- [P] posterior subscapular cataract (range 0.1 to 5.9)

For all endpoints a value of 0.1 represents a completely clear or colourless lens. Baseline will be taken as the last available non-missing assessment prior to first study drug administration. For subjects who do not have a baseline measurement for LOCS III but have a baseline anterior segment assessment which confirms no opacity in the lens, then it will be assumed that there were no abnormal lens findings at baseline and a value of 0.1 will be assigned to each of the endpoints. If the baseline anterior segment assessment does not confirm opacity of the lens or is missing then the baseline for the LOCS III endpoints will be taken as missing.

The change from baseline in each of the endpoints will be assessed.

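### The graded lens table in SAP 11.5 counts only phakic subjects who received a LOCS III grade at some point on study, so its arm contrast can be hidden, reversed or inflated

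*SAP*

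**What the plan says.** SAP 4.3.5 makes LOCS III a conditional assessment. Its condition reads "If an abnormal lens finding is noted during the anterior segment (slit lamp) examination, at any visit", and its consequence reads "then the finding should be further characterized with LOCS III". Once triggered it continues: "All subsequent visits for that subject will include LOCS III". The footnote to the Protocol section 2 flow charts has the same rule.

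For a subject with no LOCS III at baseline whose slit-lamp examination then confirmed a clear lens, SAP 4.3.5 says that "a value of 0.1 will be assigned to each of the endpoints". It explains that "a value of 0.1 represents a completely clear or colourless lens". The rule covers baseline only. Nothing assigns a score to a clear lens at a later visit.

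SAP 11.5 then summarizes observed values and change from baseline by arm and time point. Its denominator rule is "The denominator for this summary will be the subset of phakic subjects who have a LOCS III assessment performed at any time", meaning any point on study, before or after dosing. A count of pseudophakic and aphakic subjects is shown as well, without separating those in that state at baseline from those who reach it on study. SAP 4.3.5 states that "grading will not be assessed for pseudophakic and aphakic subjects as they do not have opacity".

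**The concern.** A phakic eye gets into this table in one of two ways: it has a lens finding at baseline, or it acquires one after randomization. The second way is the harm that a lens safety table should measure. Eyes that remain clear, whose true change is zero, drop out of every row. The mean shown is therefore change among graded eyes, not change among phakic eyes, and the mix of graded eyes can differ by arm.

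A difference between arms is plausible. Protocol 4.3 names traumatic cataract as an injection risk, and Protocol 7.3.3 says that the sham procedure involves no actual injection. The chance of detection also differs by schedule: the flow charts give 15 post-dose study-eye slit-lamp visits in the monthly arms (visits 3 to 17) and 9 in the every-other-month arms (visits 3 to 11).

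At stake is the reading of the plan's only summary of graded lens change. A drug that produces extra opacities could look neutral, better or worse than it is in this table, depending on which eyes are being mixed.

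**Working it through.** The documents state no figure for LOCS III, for the share of phakic eyes or for lens findings at baseline, so there is no planned figure to reproduce. The inputs below are assumptions chosen to show the range.

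**Inputs**
- p: share of phakic eyes with a lens finding at baseline (varied from 0 to 1).
- q: share of baseline-clear eyes with a new lens finding on study (assumed 0.10 on sham, 0.30 on drug).
- cp: mean LOCS III change in eyes with a baseline finding. ci: mean change in eyes with a new finding, measured from the assigned 0.1. Both are taken as equal across arms, so the drug acts only by raising q.
- Eyes that stay clear are held at 0.1, so their change is zero.

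**Formulas**
- Planned mean = [p·cp + (1-p)·q·ci] / [p + (1-p)·q].
- All-phakic mean = p·cp + (1-p)·q·ci.
- Let w = (1-p)·q / [p + (1-p)·q], the share of graded eyes with a new finding. The planned mean is then cp + w·(ci - cp), so the planned contrast (drug minus sham) is (w_drug - w_sham)·(ci - cp).
- The all-phakic contrast is (1-p)·(0.30 - 0.10)·ci.

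The planned contrast thus takes the sign of ci - cp. It is zero when ci = cp. It is also zero when p = 0, because w is then 1 in both arms. The all-phakic contrast is positive whenever ci > 0 and p < 1.

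**One case in full** (p = 0.25, cp = 1.0, ci = 0.4)
- Sham: numerator 0.25 + 0.75 × 0.10 × 0.4 = 0.28; denominator 0.25 + 0.075 = 0.325; planned mean 0.862.
- Drug: numerator 0.25 + 0.75 × 0.30 × 0.4 = 0.34; denominator 0.25 + 0.225 = 0.475; planned mean 0.716.
- Planned contrast -0.146. All-phakic contrast 0.34 - 0.28 = +0.060.
- If there were 40 phakic eyes per arm (also assumed), 13 sham eyes and 19 drug eyes would be graded.

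**Range**

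| p | cp | ci | Planned contrast | All-phakic contrast | Reading |
|---|---|---|---|---|---|
| 0 | any | 0.4 to 1.4 | 0.00 | +0.08 to +0.28 | hidden |
| 0.5 | 0.5 | 0.5 | 0.00 | +0.05 | hidden |
| 0.5 | 0.6 | 0.4 | -0.028 | +0.040 | reversed |
| 0.25 | 1.0 | 0.4 | -0.146 | +0.060 | reversed |
| 0.25 | 0.2 | 1.4 | +0.291 | +0.210 | inflated, right direction |
| 0.9 | 0.2 | 1.4 | +0.026 | +0.028 | negligible bias |
| 1 | any | any | 0 | 0 | no bias |

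The set of eyes also shifts over time within an arm. An eye clear until its trigger visit has an assigned baseline but no score at the visits in between.

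**The case against.** The best defence is that the table is openly a subset summary. LOCS III exists to characterize a finding once it is made, no test is planned, and severity among affected eyes beside a separate incidence table is a legitimate display. The incidence information is there. SAP 4.3.3 and 11.3 tabulate any lens opacity by arm and visit for the study eye, whether or not LOCS III was done. SAP 11.1 tabulates study-eye treatment-emergent events by preferred term and by severity. Each continuous summary shows its n, and all LOCS III data are listed with assigned baselines flagged.

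Most of this stands, and it limits the point. A reader might infer that the plan would miss a cataract signal. The documents do not support that, because an excess of new opacities could still appear in those other tables. A reader might also infer that the table covers only eyes with a lens finding before treatment. It does not: first findings after dosing count too, and that is where the problem arises.

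The defence does not rescue the table itself. It presents change from baseline by arm, which invites an arm comparison, and it includes newly affected eyes through the 0.1 rule while leaving out their clear counterparts. The opacity table is yes/no, mixes baseline and new opacities, has no planned shift from baseline and uses the MITT population. It cannot supply the graded comparison.

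A second objection concerns the remedy. Scoring every ungraded eye without opacity as 0.1 would treat an eye that had cataract and then lens replacement as clear. That is right, and the fix must exclude such eyes from the rule. SAP 4.3.3 also fills in some missing lens responses as no opacity, so added 0.1 values need a flag.

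**Conclusion.** The point holds for the LOCS III summary in SAP 11.5 and no further. Its denominator depends partly on a lens outcome after randomization, so its arm contrast does not estimate the difference in lens change among phakic eyes.

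It would be tempting to conclude that the table favours APL-2. The documents do not support a fixed direction. If new opacities change less than those present at baseline, the contrast can be reversed. If the two change equally, or no phakic eye has a finding at baseline, it is hidden. If new opacities change more, which the assigned 0.1 baseline may well encourage, the table points the right way and may overstate the difference. In the illustrations, planned contrasts of -0.146 to +0.291 sit beside all-phakic contrasts of +0.060 and +0.210 respectively. These figures rest wholly on assumed rates and changes, and on a drug effect that acts only through new findings. If nearly all phakic eyes have a finding at baseline, the bias is negligible.

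This is a flaw in one descriptive safety table. It is worth correcting because the correction is cheap, but it does not touch the primary analysis or the other lens and adverse event summaries.

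**What to change.** Amend SAP 4.3.5 and 11.5 as follows:
1. Use as denominator all safety-population subjects whose study eye is phakic at first dose.
2. Extend the existing 0.1 rule to post-baseline visits where the eye is still phakic, the slit lamp confirms no lens opacity and LOCS III was not done. Flag these values as imputed.
3. Assign no 0.1 after an on-study change to pseudophakia or aphakia. Count those eyes by arm, separately from eyes already pseudophakic or aphakic at baseline.
4. Show by arm the number of phakic eyes, the number graded, and the number with a first lens finding after dosing.
5. Keep the graded-only summary as a supportive display, labelled as conditional on grading.

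The cost is SAP wording and one reprogrammed table. The drawback is that the new means include imputed clear-lens values and blend incidence with severity, which is why items 4 and 5 belong beside them. No new data are needed, because the slit-lamp examination is already scheduled at every post-dose visit.

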### **11.6. LABORATORY EVALUATIONS**

Observed and change from baseline clinical laboratory data (hematology, chemistry and urinalysis) will be summarized by treatment group and protocol specified time points. Urinalysis categorical data will also be summarized by treatment group and protocol specified time points. Descriptive statistics will be used for continuous data and frequency counts and percentages for categorical data. A shift table from baseline, by treatment group and protocol specified time points, of normal, abnormal low, abnormal high and missing records will also be summarised for hematology and chemistry data with marginal totals using frequency counts and percentages.

All individual laboratory results will be listed by treatment group. The listing will include change from baseline values and values outside the laboratory reference range will be flagged.

### **11.7. ANTIGENICITY DATA**

Summaries of antigenicity data (titre, specificity and immuno-reactivity) by treatment group and protocol specified time point will be presented. Descriptive statistics will be used for specificity data and frequency counts and percentages for titre (< 5 or 5) and immuno-reactivity (non-reactive or reactive) data.

Antigenicity data will be listed by treatment group.

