4.1.3.2 Toxicology

Local toxicity

A 9-month (39 weeks) chronic repeat-dose toxicology study was done to determine the potential toxicity, antigenicity, and toxicokinetic profile of APL-2 when administered to cynomolgus monkeys by IVT injection every 4 weeks for 36 consecutive weeks at doses of 3.1, 12.4, and 24.8 mg/eye.

All animals survived through to Test Week 39. There were no test article effects on clinical observations, body weights, food consumption, hematology, clinical chemistry, CH50, macroscopic pathology or organ weights. APL-2 was minimally antigenic as evidenced by one mid-dose monkey had a marginal titer of 1:20 to APL-2 during week 39 and one monkey the high dose group was found to have low titer 1:100 antibodies to APL-2 during week 13 and 1:500 titer during week 39. There were no test article effects on any ophthalmological parameters monitored, which included indirect and slit lamp, spectral domain optical coherence tomography (SD-OCT), electroretinography (ERG), and tonometry.

Two APL-2 mid-dose animals and one APL-2 high-dose animal exhibited marked inflammation post IVT injection in one eye after the first and third injection, respectively. The inflammation gradually diminished in subsequent weeks upon proper treatment with anti-inflammatory drugs and/or antibiotics. These changes are consistent with incidental inflammation associated with IVT injection procedures and were concluded not to be drug-related.

The ERG responses were normal for both eyes of all animals at baseline, and remained within normal limits through Week 39. No drug-related changes in IOP were observed in any group through Week 39. Spectral domain optical coherence tomographic examinations revealed no APL-2 associated retinal changes. Decreases in macular volume, ≥ 1.5 but ≤ 3 and > 3 mm³, were observed in one vehicle control and one high-dose monkey, respectively. Decreased retinal thickness was observed in vehicle control and PEG40 monkeys but not in APL-2 dosed animals. A single mid-dose animal exhibited an increase in central retinal thickness of > 40 μ m.

in the left eye and an increased central retinal thickness ≥ 20 but ≤ 40 μm in the right eye. These changes were not considered APL-2-related.

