### **4.3.6. Other Safety Endpoints**

Safety will also be assessed through vital signs, laboratory safety data and antigenicity data. Changes from baseline will be calculated taking baseline as the last measurement prior to the first injection.

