## Statistical Analysis Plan

---

In general, all summary tables will display the treatment groups in the above order except for cases where it's more convenient for comparison purposes to layout the Sham Pooled group with both AMP-2 Monthly and APL2- EOM groups on the same page. In by-visit summary tables the baseline will be summarized using all available data, but also for each visit using only the baseline data from subjects with available data at the visit.

All data will be listed. Data listings will be presented by treatment group. Data listings will present study days in addition to dates, where study day is derived as (assessment date – first day of dosing) +1. The first day of dosing will be identified as Study Day 1. The analysis visit (derived from visit windowing – refer to Section 6.3) alongside the actual visit and the time since last dose will also be included in relevant listings.

All statistical analyses will be performed using SAS® (Version 9.4 or higher, SAS Institute Inc., Cary, NC, USA).

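### SAP 11.7 summarises antibody data by visit only, so the planned tables do not show how many subjects became antibody-positive after dosing, and the change from baseline in SAP 4.3.6 is not carried through

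*SAP*

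**What the plan says.** SAP 4.3.6 makes antigenicity a safety endpoint: "Safety will also be assessed through vital signs, laboratory safety data and antigenicity data". The next sentence applies to all three data types: "Changes from baseline will be calculated taking baseline as the last measurement prior to the first injection".

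SAP 11.7 then sets out the analysis: "Summaries of antigenicity data (titre, specificity and immuno-reactivity) by treatment group and protocol specified time point will be presented". Specificity gets descriptive statistics. Titre and reactivity get "frequency counts and percentages for titre (< 5 or 5) and immuno-reactivity (non-reactive or reactive) data". Individual results are covered by "Antigenicity data will be listed by treatment group", in line with the general rule in SAP 6.1: "All data will be listed. Data listings will be presented by treatment group".

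SAP 11.7 mentions no change from baseline, no shift from screening, no definition of a treatment-emergent or boosted response, and no count of subjects reactive at any time after dosing.

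**The concern.** For a drug given 7 or 13 times, the basic immunogenicity question is how many subjects without antibodies before dosing have them at some point afterwards, and how that compares with sham. A by-visit percentage reactive answers a different question, namely how many are reactive on that day. It pools subjects who were reactive at screening with those who became reactive on study. If responses come and go, different subjects may make up the count at different visits.

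The protocol gives some reason to look. In the nine-month intravitreal monkey study (Protocol 4.1.3.2), one high-dose animal was "found to have low titer 1:100 antibodies to APL-2 during week 13 and 1:500 titer during week 39". At stake is a clear safety statement on antibody formation by arm, with sham supplying the assay's background rate. Without a stated definition, readers would have to build that result by hand from listings.

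**Working it through.** **Step 1. Does SAP 11.7 deliver what 4.3.6 promises?** Compare the three data types that 4.3.6 names:
- Laboratory data (SAP 11.6): observed values and change from baseline, and for hematology and chemistry also "A shift table from baseline, by treatment group and protocol specified time points, of normal, abnormal low, abnormal high and missing records".
- Vital signs (SAP 11.8): observed values and change from baseline.
- Antigenicity (SAP 11.7): by-visit summaries and a listing, with no change from baseline.

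The omission is specific to antibodies. The SAP also knows how to count subjects across visits: section 11.2 counts subjects with post-injection IOP of 30 mmHg or more both by visit and over the whole study.

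**Step 2. How many antibody samples are there?** From the flow charts in Protocol section 2:
- Monthly arms: screening + Day 7 + 12 injection visits (Days 30 to 360) + Days 450 and 540 = 1 + 1 + 12 + 2 = 16, of which 15 are post-dose.
- EOM arms: screening + Day 7 + 6 injection visits (Days 60 to 360) + Days 450 and 540 = 1 + 1 + 6 + 2 = 10, of which 9 are post-dose.

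Protocol 9.9 gives the same pair, 10/16, although its note labels the order as monthly/EOM, the reverse of the flow charts. I use the flow charts. No Day 0 sample is scheduled, so screening is the only pre-dose sample and serves as baseline.

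**Step 3. What do by-visit counts say about subjects ever reactive?** Suppose k of n subjects are reactive at each of V post-dose visits. If they are always the same subjects, k were ever reactive. If they are different each time, min(n, k × V) were. The by-visit table looks identical in both cases. Take n = 80 per APL-2 arm (SAP 3.3), with full attendance and k assumed:

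| k per visit | Monthly, V = 15 | EOM, V = 9 |
|---|---|---|
| 1 | 1 to 15 (1.25% to 18.75%) | 1 to 9 (1.25% to 11.25%) |
| 2 | 2 to 30 (2.5% to 37.5%) | 2 to 18 (2.5% to 22.5%) |
| 4 | 4 to 60 (5% to 75%) | 4 to 36 (5% to 45%) |

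**Step 4. Add subjects reactive at screening.** Suppose 4 of 80 are reactive at screening and 4 at every later visit. If they are the same four throughout, nobody is newly reactive. If the screening four become non-reactive and each visit has different subjects, new responders number min(76, 4 × 15) = 60 in the monthly arm and min(76, 4 × 9) = 36 in the EOM arm. So the same table is compatible with 0 to 60, or 0 to 36, treatment-emergent responders.

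These are logical bounds and not forecasts. They show that the planned summaries do not determine the quantity of interest.

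**Step 5. Titre.** If the upper class means 5 or more, and if the trial assay used the same scale as the monkey study, the rise from 1:100 to 1:500 (500/100 = 5-fold) would stay within one class. Neither condition is stated in the documents, so this step is conditional; Steps 1 to 4 do not depend on it.

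**The case against.** The other side has several good points.

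- **Individual data are listed.** A reader might infer that a rise in antibodies would be invisible. It would not be: SAP 6.1 and 11.7 both provide listings, and an ever-reactive count could be derived from them later. This stands. The gap is in the summaries.
- **Not every planned output can be seen.** The SAP's table and listing indexes (sections 15 and 16) are not in the text reviewed, and the SAP refers to separate table shells. It cannot be said that such a count is planned nowhere, only that 11.7 does not describe one.
- **Baseline and sham are partly covered.** Under SAP 6.1, by-visit tables also show baseline for the subjects present at each visit, and summaries include pooled sham. That gives an aggregate comparison, but still does not identify who changed status.
- **The titre categories may lose nothing.** The printed classes may be the only values the assay returns, or a sign may have been lost when the PDF was read. The wording should not be called an error.
- **Specificity is summarised as a continuous variable.** The documents do not define it, so whether it would reveal a rising response is unknown.
- **The monkey titres are weak evidence.** It is tempting to say that 1:20 to 1:500, a 25-fold range, collapses into one class. That range spans two animals, no passage links the scale to the trial assay, and Protocol 4.1.3.2 itself regards APL-2 as only minimally antigenic.
- **The endpoint is descriptive.** No test or decision rule depends on it, and it is not among the secondary safety endpoints listed in the protocol synopsis, though Protocol 5.5 says those lists are not limiting.

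What remains is that 4.3.6 is not carried through, and that no treatment-emergent definition or cross-visit count is given in 11.7.

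**Conclusion.** The point holds as a reporting gap in a safety endpoint. The summaries in SAP 11.7 do not deliver the change from baseline in 4.3.6. They neither determine how many subjects developed antibodies after dosing nor separate them from subjects reactive at screening. With one reactive subject at each visit, the number ever reactive lies between 1 and 15 of 80 in the monthly arm and between 1 and 9 of 80 in the EOM arm, assuming full attendance.

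A reader might go further and conclude that the tables understate antibody incidence by a known factor. For example, if 10% of monthly subjects respond and each is reactive at 3 of 15 samples, average by-visit prevalence is 10% × 3/15 = 2.0%, one fifth of incidence. The documents do not support that as a finding. Both the 10% and the duration are assumed. The same inputs give 10% × 3/9 = 3.3% in the EOM arm, and if responses persist, prevalence at late visits approaches incidence. The supportable statement is that the number is undetermined, not that it is understated by a given amount.

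Sample size, power, alpha and the efficacy analyses are unaffected. The change is worth making because it is cheap and brings antibodies into line with how the SAP treats laboratory shifts and IOP.

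**What to change.** In SAP 11.7, add one subject-level table on the safety population and keep the by-visit table.

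- **Definition:** treatment-emergent reactivity means non-reactive at screening and reactive at any post-dose sample.
- **Content:** n (%) by arm, with each APL-2 arm beside its same-schedule sham as well as pooled sham. The same-schedule comparison matters because monthly subjects have 15 chances to test reactive and EOM subjects 9, so background reactivity accumulates differently.
- **Denominator:** subjects with at least one post-dose antibody sample. Show separately the number reactive at screening.
- **If the assay reports graded titres:** also give peak titre, and the number of screening-reactive subjects with a boosted titre, using a fold-rise threshold chosen to suit the assay and fixed in advance. If only two titre values exist, say so and omit this part.
- **Timing:** SAP V3.0 was written after the 12-month results were reviewed, so state whether antibody results were already known when the definition was set.

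The cost is a short definition and one extra table from samples already scheduled in every arm. The downside is that the reported number will be at least as large as the number newly reactive at any single visit, and should be read against the same-schedule sham.
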